Trial Participants	Preoperative elective colorectal patients (Group 1, n=16) Postoperative emergency patients (Group 2, n=8) General abdominal surgical ements) All patients will be over 60 year	Preoperative elective colorectal or pancreatic cancer patients (Group 1, n=16) Postoperative emergency patients presenting with cancer (Group 2, n=8) General abdominal surgical emergencies (Group 3,	
Planned Sample Size	32		
Treatment duration	1 month		
Planned Trial Period	2 months	2 months	
	Objectives	Outcome Measures	
Primary	To assess the palatability of a nutritional supplement for surgical patients	Whether patients can take the supplement	
Secondary	To assess compliance to supplementation regime and impact on body composition	1. Whether the supplement impacts patient appetite (Groups 1, 2 & 3) 2. Whether supplementation affects body composition (Group 1)	
Formulation, Dose, Route of Administration	Nutritional supplement gel to b	Nutritional supplement gel to be taken orally.	

iv. FUNDING AND SUPPORT IN KIND

FUNDER(S)	FINANCIAL AND NON FINANCIALSUPPORT
(Names and contact details of ALL	GIVEN
organisations providing funding and/or	
support in kind for this trial)	
Vitrition UK Ltd	65 gram nutritional supplement gel. Product
	specification QD27 V8.2.25.04.2017

v. TRIAL FLOW CHART

Background

Surgical resection of colorectal and pancreatic cancer is usually undertaken as a curative procedure but these operations are major undertakings and approximately half of the patients can suffer with debilitating postoperative complications (van Rooijen et al., 2019). The physical impact of surgical intervention has been reduced, with modern surgical and anaesthetic techniques, reducing morbidity post operatively, but the patients presenting for cancer surgery tend to be in an older age group, with 50% being over 65 years of age. As people age they are more likely to become frail, and the presence of frailty syndrome (a multisystem disease process that reduces the ability of an individual to respond to stressors) is well documented to be associated with worse surgical outcomes (Tan et al., 2012). Complications, length of hospital stay, and mortality rates also increase with age and frailty (Makary et al., 2010), whilst the nutritional status of older patients is an independent predictor of survival rates (Ommundsen et al., 2014).

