suffer from frailty and sarcopenia, are able to consume novel gel and protein-based nutritional supplements without reducing their appetite. Preliminary data also showed that nutritional supplementation over a three-month period improved functional performance (Ispoglou et al., 2017, Butterworth et al., 2019) and body composition (Ispoglou et al., 2016) of older people. This approach, using a novel nutritional supplement, is potentially an ideal way to improve protein and energy intake in these patients. However, this approach has not been tested in patients with intestinal cancer. We do not currently know whether the nutritional supplement is acceptable to, and can be taken by, these patients as means to enhance protein and energy intakes. We therefore wish to investigate a group of elective preoperative cancer patients, a group of post-operative cancer patients, and a group of emergency patients. This latter group often present in a frail condition, and do not have the opportunity to improve their health before they undergo emergency surgery. In addition to measuring the acceptability of the supplement to patients, we plan to use non-invasive techniques (bioelectrical impedance, hand grip strength and a 'get up and go test") before and after a short-term supplementation period (4 weeks) to gather evidence of its efficacy

Aims and Objectives

The research team aim to investigate the feasibility and acceptability of novel nutritional supplementation in bowel/pancreatic cancer patients preoperatively and patients who have emergency bowel surgery or planned colorectal cancer surgery postoperatively.

The project will be conducted in two parts: part A and part B. In part A of the feasibility study the key research question the research team will aim to answer is:

"Does consumption of a nutritional gel (65 ml) before an 'ad libitum' breakfast (eat as much as someone can eat) negatively affect appetite and energy intake compared to a breakfast alone (control)?"

The key outcomes measured will be nutritional intakes, appetite and palatability perceptions at the breakfast.

In part B of the feasibility study the key research question the research team will aim to answer is:

"Can participants (who also completed part A) consume two supplements daily over a longer period of time without compromising their ability to eat food?"

The key outcomes measured will be habitual nutritional intakes and monitoring compliance to the supplementation regime.

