A secondary question for participants in part B will be:

"Can short-term supplementation improve body composition and aspects of physical fitness?"

The secondary outcomes measured will be fat mass and fat free mass as measured by bioelectrical impedance, handgrip strength test and a get-up and go test.

Design

A) Participant Recruitment

There are three main groups of participants who will be included in the study, who will be male and female patients over the age of 60, are:

- 1) Bowel (n=8) or pancreatic cancer patients (n=8) planned to undergo (elective) surgery. Part A and B will need to ideally be completed before surgery. These planned surgical patients, once they have completed part A of the feasibility study, will complete part B (i.e. they will be asked to take a nutritional supplement twice a day for 4 weeks and as preparation for their impending surgery).
- 2) Bowel cancer patients who have undergone elective surgery (n=8). Part A and B will be completed after surgery. After they complete Part A, these surgical patients will be asked to take part in part B of the study (i.e. take the supplements for 4 weeks) once they have a return of bowel function and have begun tolerating diet and fluids as assessed and documented by a surgeon during daily post-operative review.
- 3) Patients undergoing emergency surgery from a range of clinical conditions (n=8). Part A and B will be completed after surgery as these patients cannot be assessed pre-operatively due to the urgent requirement for surgery. After they complete Part A, these emergency surgical patients will be asked to take part in part B of the study (i.e. take the supplements for 4 weeks) once they have a return of bowel function and have begun tolerating diet and fluids as assessed and documented by a surgeon during daily post-operative review.

B) Methodology

The two parts of the feasibility study are as follows:

Part A of feasibility study (Palatability and Appetite Assessment)

The experimental trial will involve consumption of an ad libitum breakfast and consumption of a 65 g essential amino acid based nutritional prototype 10 minutes before the ad libitum breakfast (intervention) or no additional gel supplementation(control). All patients will complete a control and an intervention visit. The patients will complete an appetite assessment for intervention and control visits (2 separate visits) and a palatability assessment for the intervention visit.

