The outcomes we will be measuring in all three groups are nutritional intakes, appetite and palatability perceptions at the breakfast.

The gel is the intervention and is manufactured by Vitrition UK Ltd (Product specification QD27 V8.

2. 25. 04. 2017.) See below composition per 65 grams gel:

Energy = 113.65 kcal, Carbohydrates = 21.936 grams, Protein: 7.5 g and all in the form of essential

amino acids, Sugars = 13.36 grams, Fats = 0 grams, Salt = 0.026 grams, 500 iu of vitamin D3.

The ad libitum breakfast will have an energy density of 4.9 kJ/g and a macronutrient composition of

59% carbohydrate, 18% protein and 23% fat. Meal preparation will involve mixing of 54 g of porridge

oats (Oatso Simple Original, Quaker Oats) with 292 ml semi-skimmed milk. The mixture will then be

cooked in a microwave for two and a half minutes at 700 W. Patients will need to consume the

breakfast in isolation to avoid any social influence on food intake. A bowl of the breakfast meal will

be provided by one of the investigators or a trained nurse and patients will be instructed to eat until

'comfortably full', with no time limit set for eating. This bowl will be replaced before the participant

empties it. Food intake will be calculated as the weighted difference in food before and after eating.

Appetite perceptions (hunger, satisfaction, fullness and prospective food consumption) will be

measured using 100 mm visual analogue scales with descriptors anchored at each end. A composite

appetite score will be calculated as the mean value of the four appetite perceptions after inverting

the values for satisfaction and fullness. Palatability ratings (visual appeal, smell, taste, aftertaste and

pleasantness) will be obtained for the supplements and the ad libitum breakfast. A composite

palatability score will be calculated as the mean value of the palatability subscales.

Part B of Feasibility study (Supplementation regime compliance and body composition)

Following completion of Part A, patients will be given 56 gels (to cover 4 weeks of supplementation,

twice daily (one gel alongside breakfast and one alongside their lunch meal). The patients will also

be given a 1 x3 day food diary to complete at home in week 3 of the supplementation intervention.

Outcome measures include:

• Nutritional intakes in a food diary.

Monitoring compliance to the supplementation regime.

Body composition assessment (measured by bioelectrical impedance) at the start and end of

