final visit to Leeds Beckett campus) bringing their completed food diary and any spare gels on this

visit. They will repeat the physical assessments described above on this final return visit.

GROUP 2 & 3 (postoperative cancer patients and postoperative emergency patients):

Project Proposal IRAS ID: 280595

These two groups will complete Part A - palatability test and consume an ad libitum breakfast

following their surgery during their hospital stay. They will not complete a second breakfast meal

assessment. They will be assessed by a senior member of the surgical team who will decide if their

bowel function has returned sufficiently to begin eating and drinking before they commence in part

A.

These two groups will not be required to perform an overnight fast before the palatability test and

will only complete the palatability/appetite test once.

No physical health assessments will be undertaken by group 2&3.

They will then enter Part B of the study and be given gel supplementation at breakfast and lunch

each day whilst they are recovering in hospital. They will continue the supplementation at home for

a total of 4 weeks and will complete a 3 day food diary during week 3 of the study. When these

patients return for their postoperative outpatient review at 4 weeks following their procedures, the

food diaries and spare gels will be collected by the research team.

Compliance to the regime will be monitored by counting any gels that have not been consumed. The

food diaries will be collected in both groups and stored on site at St James's University Hospital. The

diaries will be transcribed onto an electronic document that will be stored securely on Leeds

Teaching Hospitals Trust servers in a password protected hard drive area. The paper diaries will be

destroyed via the confidential waste system as per NHS protocols for information governance.

Eligibility

The elective patients presenting with cancer, will be identified and selected at the multidisciplinary

meetings by the colorectal and pancreatic consultant surgical team. The patients to be included in

the study will all be over 60 years old and will be subject to the following inclusion criteria:

• Patient has capacity to understand the study and give informed consent

• Patient is capable of ingesting the oral supplement

A senior member of the surgical care team will approach the patient either after diagnosis has been

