discussed with the patients for the planned colorectal/pancreas cancer patients. The emergency

patients will be identified by the National Emergency Laparotomy Audit (NELA) team within the

hosting organisation (Leeds Teaching Hospitals Trust). A senior clinician will assess the suitability of

the patient to inclusion into the study whilst an inpatient on the surgical ward at least 48 hours

following emergency surgery.

Patients will be excluded from the study if they meet the following criteria:

Project Proposal

Patient is incapable of understanding the study and giving informed consent

Patient is incapable of ingesting the oral supplement

• Patients with the very rare potential complication of an allergy to nutritional supplement

(sodium benzoate or sodium metabisulphites).

Data Analysis

Part A

Appetite perceptions (hunger, satisfaction, fullness and prospective food consumption) will be

measured using 100 mm visual analogue scales with descriptors anchored at each end. A composite

appetite score will be calculated as the mean value of the four appetite perceptions after inverting

the values for satisfaction and fullness. Palatability ratings (visual appeal, smell, taste, aftertaste and

pleasantness) will be obtained for the supplements. A composite palatability score will be calculated

as the mean value of the palatability subscales.

Part B

Group 1 patients will have body composition assessment (measured by bioelectrical impedance) and

functional capacity will be measured by assessment of handgrip strength test and a 'get up and go'

test. These physical assessments will be measured twice during the study; at the start during the

second visit (Day 1 of supplementation) and at the end of the supplementation intervention (after 4

weeks).

Part B will focus on daily supplementation during a breakfast and lunch time meal for 4 weeks. The

patients in all three groups will be asked to complete a paper food diary for 3 days during the third

week. The Group 1 patients will return to the laboratory after 4 weeks bringing their diaries and any

spare gels on this visit. Group 1 patients will repeat the physical assessments described above on

this final return visit. The Group 2 & 3 patients will bring unused gels and food diaries with then to

the post-operative clinical review at St James's University Hospital.

Data Management

The research is sponsored by the University of Leeds and the researchers will undertake research

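### In Groups 2 and 3 both key Part B outcomes reach the team only through attendance at the 4-week outpatient review, with no fallback, so losses are probably illness-related and compliance probably overstated

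*Protocol*

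**What the plan says.** Aims and Objectives names the Part B outcomes: "The key outcomes measured will be habitual nutritional intakes and monitoring compliance to the supplementation regime". Compliance has one measure, given at the end of the Group 2 & 3 pathway: "Compliance to the regime will be monitored by counting any gels that have not been consumed". Intake comes from a single 3-day diary kept in week 3, which the Part B description expects to be filled in at home.

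For Groups 2 and 3 the hand-over point is the clinic: "patients return for their postoperative outpatient review at 4 weeks following their procedures, the" diaries and leftover gels are collected then ("food diaries and spare gels will be collected by the research team"). Data Analysis, Part B, repeats the arrangement: "The Group 2 & 3 patients will bring unused gels and food diaries with then to" the postoperative clinical review. Neither place describes a telephone, postal, ward or home alternative, and neither says how a patient who does not come is to be scored. Group 1 likewise returns both items at one final laboratory visit.

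On supply, the Part B description says: "Following completion of Part A, patients will be given 56 gels (to cover 4 weeks of supplementation", taken twice daily. Ethical Considerations has the postoperative and emergency patients starting 48 hours after surgery. Participant Recruitment makes the start conditional on return of bowel function and on tolerating diet and fluids.

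**The concern.** The Part B question is whether patients can take two gels a day without eating less. The patients most likely to show that they cannot are those who recover poorly, and poor recovery is also a likely reason for missing a clinic review. The collection arrangement therefore ties being observed to the condition that probably governs the outcome.

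The protocol makes this plausible. It describes emergency patients as often frail. It gives an inpatient stay of about 7 days only where there are no complications. It also says that after colorectal or pancreatic cancer resection "approximately half of the patients can suffer with debilitating postoperative complications".

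At stake is whether the compliance and intake results describe everyone given gels or mainly those who recovered well. A later trial is meant to build on these results. An analysis plan can choose a denominator or compute bounds, but it cannot supply a count or a diary that was never obtained.

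**Working it through.** **Inputs from the protocol**
- Group 2: 8 patients (Participant Recruitment: "Bowel cancer patients who have undergone elective surgery (n=8"). Group 3: 8 patients (same list). Together 16.
- Planned total: 16 + 8 + 8 = 32, which agrees with the trial summary.
- Gels per patient: 4 weeks × 7 days × 2 a day = 56, which agrees with the stated supply.
- The protocol gives no attendance rate, expected compliance or compliance threshold. Everything below that uses such a rate is an assumption.

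**Weight of one non-attender.** 1/16 = 6.25% of the Group 2 and 3 data for both outcomes.

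**Selection.** Let k of 16 not attend, attenders take a share a of their gels, and non-attenders a share m. The attender-only figure is a. The figure for all patients is ((16 − k) × a + k × m)/16. With a = 90% assumed:

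| k | m = 0% | m = 30% | m = 90% | m = 100% |
|---|---|---|---|---|
| 2 | 78.8% | 82.5% | 90.0% | 91.3% |
| 4 | 67.5% | 75.0% | 90.0% | 92.5% |
| 6 | 56.3% | 67.5% | 90.0% | 93.8% |

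For example, with k = 4 and m = 30%: (12 × 0.90 + 4 × 0.30)/16 = (10.8 + 1.2)/16 = 75.0%. At m = 30% the attender-only 90% is too high by 7.5, 15.0 or 22.5 points. At m = 90% the bias is zero. At m = 100% the attender-only figure is slightly too low. The last column is also what would be reported if a return that never arrived were read as no gels left over, because compliance is inferred from leftovers.

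**Timing, a separate effect.** Take the review as day 28 after surgery and count all 56 gels as due by then.
- Start on day 2: (28 − 2) × 2 = 52 gels can have been taken, so a perfect complier scores 52/56 = 92.9%.
- Start on day 7 (assumed): (28 − 7) × 2 = 42 gels, so a perfect complier scores 42/56 = 75.0%.

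**Both effects together**, with attenders taking 90% of gels due, k = 4 and m = 30%, so that the figure for all patients is 75.0%:
- Day-2 start: measured 0.90 × 52/56 = 83.6%, net error 83.6 − 75.0 = +8.6 points.
- Day-7 start: measured 0.90 × 42/56 = 67.5%, net error 67.5 − 75.0 = −7.5 points.

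Selection alone pushes compliance upward whenever non-attenders took less. The net sign depends on the start day and on the denominator. No size is attempted for dietary intake, because the protocol gives no figures to work from.

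**The case against.** A reader might infer that non-attenders are dropped from the analysis and that compliance is bound to look better than it is. The documents support neither inference. The protocol is silent on non-attenders, and their scoring may sit in an analysis plan that is not shown. Upward bias needs non-attenders to have taken fewer gels, which is plausible but not shown.

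Other points on that side:
- **The complication figure is not a non-attendance rate.** It concerns colorectal and pancreatic cancer resection, so it does not describe the mixed emergency conditions of Group 3, and a complication is not a missed review. It supports the mechanism for Group 2 and gives no size. For Group 3 the support is the protocol's remark on frailty.
- **Some of the sickest patients never start.** Return of bowel function, tolerance of diet and fluids and, in Group 3, a senior clinician's assessment come first. This probably reduces the loss. It does not remove it, since deterioration or readmission can follow.
- **Inpatients remain within reach.** The hospital is a research site, and gels are given on its wards. A ward count is possible there, but the protocol does not describe one.
- **Bounds can be calculated.** With 56 gels each, best and worst cases are available, and the number not returning is itself a feasibility result. With 16 patients, though, each missing count widens those bounds by 6.25 points, and a bound does not replace a count.
- **Group 1 also uses a single return visit.** That is true, and the fallback should cover it. Group 1 should ideally finish before surgery, so postoperative illness would not normally govern its attendance.
- **Timing can pull measured compliance down.** This stands. It affects attenders' scores and does not bring missing patients back, so it does not cancel the problem.

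**Conclusion.** The point holds in a limited form. For half the planned sample, one clinic attendance is the only described source of both key Part B outcomes, and nothing is provided for patients who do not attend. That is a data-collection choice fixed in the protocol, not a detail left to the analysis plan. Loss is probably related to illness, and compliance among those seen is probably, though not certainly, higher than compliance among all patients given gels.

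The overstatement is 7.5 to 22.5 points if attenders take 90%, non-attenders 30%, and 2 to 6 of 16 do not attend. It is zero if non-attenders took as many gels as attenders. These rates are assumed, so the figures show sensitivity and are not a forecast. The mismatch between the review date and the length of the course is a separate fault that can lower measured compliance, so the sign of the total error is open until both are settled. The change is cheap and should be made before recruitment.

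**What to change.** - **Fallback collection.** For any patient who does not attend, take the gel count on the ward or by telephone at the planned date, and retrieve the diary by post or from the ward. Apply the same rule to Group 1's final visit.
- **Denominator.** Use every patient given gels.
- **Reporting.** State how many patients were not seen and why. Where no count can be obtained, show compliance with that patient at zero as a sensitivity bound beside the observed figure. A missing return should not be read as no gels left over.
- **Timing.** Reconcile the review 4 weeks after the procedure with the 4-week, 56-gel course that starts 48 hours or more after surgery, so that gels not yet due at the count are not recorded as missed.

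The cost should be a few telephone calls or ward visits and a few sentences in the protocol; the protocol does not describe staffing, so this is a judgement. A telephone count is less exact than a physical one, and the stated compliance may be less favourable.
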